### 5.2 Exclusion Criteria

1. Actively receiving radiation treatment
2. Medical history of heart failure, coronary artery disease or arrhythmia
3. Contraindications to cardiopulmonary exercise testing (CPET)
4. Contraindications to magnetic resonance imaging (MRI) (e.g ferromagnetic cerebral aneurysm clips or other intraorbital/intracranial metal; pacemakers, defibrillators, functioning neurostimulator devices, non-compatible MRI tissue expanders or breast implants, or other implanted non-compatible MRI devices), weight over 550 lbs, or symptomatic claustrophobia
5. Contraindications to exercise, including a history of surgery with sequelae that restrict ability to exercise safely or comfortably
6. Unwilling to complete intervention procedures or outcome measures

### 5.3 Ethnic/Gender Distribution

TARGETED / PLANNED ENROLLMENT: 30			
Ethnic Category	Sex / Gender		
	Females	Males	Total
Hispanic or Latino	2	0	2
Not Hispanic or Latino	28	0	28
Ethnic Category Total of All Subjects*	30	0	30
Racial Categories			
American Indian / Alaska Native	0	0	0
Asian	0	0	0
Native Hawaiian or Other Pacific	0	0	0
Black or African American	6	0	6
White	24	0	24
Racial Categories: Total of All Subjects*	30	0	30

## 6.0 INTERVENTION PLAN

### 6.1 Treatment Intervention Arm

Participants in the intervention group will be randomized to receive either AE or RE training. The intervention will comprise of a combination of supervised and unsupervised sessions. Supervised sessions will be led remotely via videoconferencing by a trained fitness instructor, while unsupervised sessions will involve following along with recorded videos. Training protocols will be adapted from the American College of Sports Medicine's (ACSM) guidelines and designed to progress in intensity, depending on patient tolerance.

All intervention sessions will include 5 minutes of warm up and 5 minutes of cool down. Warm up and cool down will consist of light aerobics and stretching for both groups. Sessions will occur 3 times a week, with 1 supervised and 2 unsupervised. In the first 3 weeks of resistance training, sessions will occur 2 times per week (1 supervised), to account for increased muscle soreness when starting a resistance training regimen.

Exercise intensity will be measured using the Rating of Perceived Exertion (RPE) scale, which collects respondent's perception of exertion level on a scale from 6-20. Moderate exercise will be considered a 12-13 on this scale, while 14-16 will constitute vigorous exercise.

Participants will rate their perceived exertion after each exercise session, and RPE feedback will be utilized to adjust intensity levels for participants' upcoming sessions.

#### **6.1.1 Aerobic exercise training**

Aerobic exercise sessions will entail various standard calisthenics, including such as marching in place, side steps, and jumping jacks. Participants will complete exercises in sets, performing a sequence of exercises for a certain number of seconds each (e.g. 30-60 seconds per exercise) before a rest of 60-240 seconds. The total time of each session will be at least 30 minutes and both the duration and intensity of the sessions will increase during the intervention, as outlined in Appendix D.

Intensity will be varied by adjusting the type of exercise, the number of seconds per exercise and/or the amount of rest time between sets. The intensity will progress, as tolerated, for the first 6 weeks of the intervention, starting at moderate intensity and building to sustained vigorous intensity (see Appendix D). The estimation of intensity will be based off a participant's heart rate (HR) at peak  $VO_2$  from the CPET at baseline. Trained staff will help participants to determine this target HR.

#### **6.1.2 Resistance exercise training**

Resistance exercise training will comprise of weight bearing functional tasks (e.g. sit-to-stand) and weighted exercises, with each session targeting upper and lower body large muscle groups.

Participants will complete 5 exercises in sets of 1 or 2, performing a sequence of exercises for a certain number of repetitions ("reps") each (e.g. 8-12 reps per exercise) before a short rest. Sets will be separated by a rest of 60-240 seconds.

At baseline testing, study staff will determine participants' one rep maximum for various weighted exercises. The starting weights for the intervention will be based on this measurement.

Intensity can be varied by adjusting the number of reps per set, the number of seconds of rest, or the weight being used.

#### **6.1.3 Combined aerobic and resistance exercise training**

The AE+RE intervention will involve a combination aerobic and resistance exercises within session, with approximately half of each session devoted to AE and half devoted to RE (See Appendix E). Aerobic sets will be completed before resistance sets within each session.

### **6.2 Waitlist Control Arm**

The waitlist control group will spend 24 weeks waitlisted for the intervention, during which time they will follow the same schedule of evaluations as the intervention group but will not receive exercise sessions. After completing 24-week assessments, the control group will receive a digital copy of sessions recorded during the intervention group and an outline of sessions for 24 weeks.

## 7.0 GUIDELINES FOR ADVERSE EVENT REPORTING

### 7.1 Adverse Event Reporting/Institutional Policy

In accordance with institutional policy, all adverse events which in the opinion of the principal investigator are unexpected and related or possibly related to the research and serious or suggest that the research places research participants or others at greater risk of physical or psychological harm than was previously known or recognized be reported to the IRB within 10 calendar days of learning of the problem.

Definitions:

**Adverse Event** - Any untoward medical occurrence in a participant, such as any unfavorable and unintended sign (including an abnormal laboratory finding, for example), symptom, or disease temporally associated with the intervention.

**Life-threatening Adverse Event** – Any adverse event that places the participant, in view of the investigator, at immediate risk of death from the reaction.

**Unexpected Adverse Event** – An adverse event is “unexpected” when its nature (specificity), severity, or frequency are not consistent with (a) the known or foreseeable risk of adverse events associated with the intervention; and are also not consistent with (b) the characteristics of the subject population being studied including the expected natural progression of any underlying disease, disorder or condition any predisposing risk factor profile for the adverse event.

**Serious Adverse Event (SAE)** – Any adverse event occurring that results in any of the following outcomes:

- death
- a life-threatening adverse event (real risk of dying)
- inpatient hospitalization or prolongation of existing hospitalization
- a persistent or significant disability/incapacity
- a congenital anomaly
- requires intervention to prevent permanent impairment or damage

**Attribution** - The following are definitions for determining whether an adverse event is related to a medical product, treatment or intervention procedure:

- An adverse event is **related or possibly related to the research procedures** if in the opinion of the principal investigator, it was more likely than not caused by the research procedures.

- Adverse events that are solely caused by an underlying disease, disorder or condition of the subject or by other circumstances unrelated to either the research or any underlying disease, disorder or condition of the subject are not “related or possibly related.”
- If there is any question whether or not an adverse event is related or possibly related, the adverse event should be reported.

All adverse events will be reported to the University of Washington IRB according to UW guidelines.

#### 7.1.1 Adverse Event Grading

Adverse events will be graded as Mild, Moderate, or Severe using the NCI Common Terminology Criteria for Adverse Events (CTCAE) Version 5.0 as a guide:

[https://ctep.cancer.gov/protocoldevelopment/electronic\\_applications/docs/ctcae\\_v5\\_quick\\_reference\\_5\\_x7.pdf](https://ctep.cancer.gov/protocoldevelopment/electronic_applications/docs/ctcae_v5_quick_reference_5_x7.pdf) See Appendix A, Data and Safety Monitoring Plan.

## 8.0 DATA AND SAFETY MONITORING

The Principal Investigator will meet with study staff on a monthly basis to review participant's adverse events, verify CTCAE grade, and provide attribution, and to review response data.

This study will employ a Data and Safety Monitoring Plan (DSM; see Appendix A) to outline how participant safety and confidentiality will be managed throughout the study. The PI and co-investigators have clinical licensure (RN or MD) and will review quarterly the following study data provided by the research team:

- Number of participants
- List of adverse event and responses that have occurred in the specified time frame
- Cumulative table of adverse events by type and grade, including deaths as outlined in the protocol-specific DSM
- Premature terminations of the intervention and other safety issues

At each review, the PI and co-I's will determine whether:

- The trial should continue as originally designed
- The trial should be changed
- The trial should be terminated
- Outcome results should be released prior to the reporting of the study results

## 9.0 DATA MANAGEMENT/CONFIDENTIALITY

This project's varied recruitment strategies involve different types of contact with identifiable health information prior to enrollment. Recruitment streams 2 and 3 outlined in section 4.3.1 will involve potential participants either 1) contacting the study team directly or 2) providing consent for the study

team to make contact.

Recruitment stream 1 will require viewing PHI prior to consent by SCCA breast oncology staff who routinely view this information in their normal workflow. Recruitment stream 4 will involve obtaining PHI prior to consent. The IRB will review and approve all procedures for viewing or obtaining PHI prior to consent. Women who are approached will not be undergoing any serious or sensitive treatments.

All forms of data described in previous sections will be recorded on paper or computerized data forms with no personal identifying information. Candidates for screening will be assigned a 3-digit study ID, and all data collected during screening will be stored with this ID. A 3-digit number will be assigned to each participant, once enrolled. Only the PI and HIPAA-trained study coordinator will have access to the secure OneDrive spreadsheet that links names with subject study identifiers. To ensure confidentiality, no personal identifying information will be coded on the questionnaires or sample data. A separate document will contain contact information but will not contain personal data or protected health information that is collected as part of the study. Study data will be stored in a REDCap database that only the PI and the study coordinator can access. All paper data will be stored in locked file cabinets in a locked office and on password-protected computers located behind a secure firewall.

Data are collected by team members who have completed training in human subject research, HIPAA, research integrity, research data management and confidentiality, and training to criterion on project protocol.

## 10.0 STATISTICAL CONSIDERATIONS

For objective 1, we will measure the feasibility of our intervention by calculating recruitment rates (% participants enrolled of those approached), enrollment rate (% enrolled of those eligible), lost to follow-up (% who dropped out of those enrolled), intervention discontinuation rate (% of intervention participants who permanently stop the intervention for any reason by Week 24), intervention attendance (% exercise sessions attended), relative dose intensity (% completed sessions), and compliance (based on accelerometry data, self-report of exercise via questionnaires). A benchmark to determine feasibility includes <40% loss to follow-up.

In objective 2, we will start with an analysis of the safety endpoints by calculating the number and percent of adverse events that occurred during the intervention and during the waitlist control period. This analysis will be stratified by the severity of the adverse events, the seriousness of the adverse events, and by the attribution of the adverse events.

The results from above analyses (for Study Aim 1) will be a primary consideration to inform the feasibility and safety of launching a larger scale intervention from the pilot intervention. If both these sets of data provide indications that the study is feasible and safe, then the exploration of additional intervention outcomes will take place. These data will be presented in a manuscript to describe the potential for this intervention. The following analyses will explore additional intervention outcomes to inform the intervention's potential to have an impact on CRF, functional capacity, physiologic changes, and PRO in a larger scale intervention.

Next, the analysis will explore the impact of the intervention on the outcome of CRF in intervention participants versus waitlist control participants using generalized linear models (GLM) comparing baseline to 24-week measurements. This analysis will be repeated for the additional outcomes of functional capacity, i.e., submaximal exercise capacity; physiologic changes, i.e., thigh IMF:SM, abdominal depots of fat (VAT, SQ, RP, and IP fat), and body weight; and patient reported outcomes, i.e., QOL, perceived well-being, and fatigue. These analyses will be performed according to the intent-to-treat principle, where outcomes are analyzed by intervention assigned, regardless of the level of adherence. A secondary per protocol analysis will be conducted, and these results will be reported and interpreted together with the intent-to-treat analysis. This per protocol analysis will include only those participants who (a) completed all clinic visits and who completed at least 85% of the required physical activity. In addition, this secondary analysis will investigate factors related to a lack of intervention adherence, which will include baseline measures of perceived well-being, mood disturbance, perceptions of PA, fatigue, and insomnia.

For objective 3, the analysis will explore the impact of AE vs RE vs combined AE+RE on safety outcomes using generalized linear models (GLM) comparing pre-intervention measurements to post-intervention measurements. Next, this analysis will be repeated for the additional outcomes of CRF, functional capacity, physiologic changes, and patient reported outcomes of QOL, perceived well-being, and fatigue.

In addition, we will explore potential moderators of the intervention, namely baseline BMI and physical activity, and adherence to the intervention for Objectives 2 and 3, and as guidance in designing the subsequent large-scale intervention. First, we will stratify upon BMI to explore whether the intervention showed greater benefit in those with higher BMI. Then we will repeat this for baseline physical activity to explore whether the intervention showed greater benefit in those with lower baseline physical activity. Next, the level of adherence to the intervention will be evaluated by examining the accelerometry data output in conjunction with the self-reported physical activity data. We will also conduct qualitative analyses utilizing data from the elicitation interviews conducted at the end of the intervention. This analysis will summarize data collected from the participants' into themes.

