## 4.0 STUDY DESIGN

### 4.1 Description of Study

This is a pilot study of a 2-arm randomized trial with a 2:1 initial allocation to exercise intervention or waitlist control (see Appendix B for study schema). The intervention group will then be randomly assigned (1:1) to receive either a 12-week aerobic exercise (AE) intervention or a 12-week resistance exercise (RE) intervention.

At 12 weeks, the intervention group will be assessed for intervention response, defined as a  $\geq 5\%$  increase in 6-minute walk distance (6MWD) over baseline. Non-responders to either AE or RE will receive 12 weeks of combined AE+RE. Intervention responders will continue the exercise intervention in their current assignment, either AE or RE alone, for the additional 12 weeks.

This study will employ a waitlist control. After 24 weeks, the waitlist control group will receive a digital copy of sessions provided to the intervention arm. The control and intervention arms' schedule of evaluations will be identical across all 24 weeks of the trial.

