##### *Intervention Safety*

Safety: Intervention safety will be determined by reviewing and quantifying the number of adverse events (mild, moderate, or severe), serious adverse events, and by reviewing the type and severity of adverse events attributed to study procedures among each study group. See Section 8.0 for adverse event definitions and protocols.

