#### 4.3 Study Procedures

#### 4.3.1 Recruitment

This project will recruit 30 study participants through a multi-pronged approach:

Seattle Cancer Care Alliance (SCCA) clinics: At SCCA, we will work with the breast oncology clinic research team to obtain a list of potentially eligible research participants that will include patient name, phone number, and mailing address. This eligibility will be based on age and approximate end date of chemotherapy or Herceptin therapy. Potentially eligible participants identified through SCCA will receive a mailed letter endorsed by their oncologist inviting them to call the study coordinator for more information and/or screening. The study team may follow up proactively with a phone call no less than two weeks after sending the letter.

Breast cancer support groups in the community: Study information will be provided to breast cancer support groups in the community by sharing study flyers (paper, electronic, or Web versions) with the organizers of these groups and by giving presentations at in-person group events, as permitted by organizers.

Re-contacting previous breast cancer research participants: The pool of previous breast cancer research participants will be generated from past projects under the purview of the study's principal investigators or shared from affiliate investigators. Previous participants or candidates will be contacted via phone, email, or mailed letter, depending on what information is available to the study PIs.

The UW ITHS Leaf tool: The University of Washington's Leaf system will be used to generate an identifiable cohort of potentially eligible patients in the UW Medicine system. The study will query the database for patients who meet key eligibility criteria and who have recently visited the UW Medicine system for treatment. Candidates generated from this list will be sent a letter that describes the study and invites them to contact the study team should they be interested in participation. The study team may follow up proactively with a phone call no less than two weeks after sending the letter.

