#### 4.3.4 Randomization

Participants will be randomly allocated to the intervention or waitlist control arm using blocked randomization (2:1 intervention to control), stratified upon whether the participant has received “AC” chemotherapy (doxorubicin and cyclophosphamide combination therapy). Intervention participants will then be randomized to either aerobic exercise training or resistance strength training, again using blocked randomization stratified on AC treatment history. Randomization will be performed in REDCap with the REDCap Randomization module.

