## **DATA ANALYSIS PLANS**

[figure not shown]
As this is a pilot study, there will be insufficient numbers to conduct a well-powered interim analysis. The study team will examine SAEs and expected AEs in aggregate at the midpoint of the study to examine whether disproportionate SAEs or AEs have occurred in the intervention participants. While there is unlikely to be statistical power in interim analysis, we will conduct bi-variate statistical analysis consisting of chi-square tests to evaluate the proportion of SAEs and AEs in intervention participants versus control participants. The investigators will review this statistical analysis. Discussions of whether sufficient evidence exists for stopping the trial early will involve consideration of whether the AEs are related or unrelated to the study activities.

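### Safety is summarised in adverse events with no participant or person-time denominator, so under 2:1 allocation equal risk gives twice the event count in the exercise arm

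*Combined protocol and SAP*

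**What the plan says.** Safety is a secondary outcome, and its measure is described in four places.

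- **Section 4.2.2, Intervention Safety.** Safety is determined by "reviewing and quantifying the number of adverse events (mild, moderate, or severe), serious adverse events", together with a review of the type and severity of attributed events in each study group. The unit is the event, and no denominator is given.
- **Section 10.0, objective 2.** The analysis starts by "calculating the number and percent of adverse events that occurred during the intervention and during the waitlist control period", broken down by severity, seriousness and attribution. The percent has no stated denominator.
- **Appendix A, Data Analysis Plans.** At the study midpoint, chi-square tests are used "to evaluate the proportion of SAEs and AEs in intervention participants versus control participants". The text does not say whether an observation is an event or a participant. The result goes to the investigators, who may discuss early stopping.
- **Section 10.0, objective 3.** Safety is compared across exercise modes with generalized linear models. Again no unit is given.

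The design has a "2:1 initial allocation to exercise intervention or waitlist control" (Section 4.1), with 30 participants planned (Section 4.3.1) and the same 24-week evaluation schedule in both arms. Nowhere do the documents define a percent of participants with at least one event, or a rate per participant or per unit of follow-up. By contrast, the paragraph just before the safety text in Section 10.0 names the denominator for recruitment, enrollment, loss to follow-up and discontinuation.

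**The concern.** Event totals from arms of unequal size are not directly comparable. One arm here is twice the size of the other, so an intervention that adds no risk is still expected to produce twice as many events. A beneficial effect could be hidden in the same way. A single participant with repeated mild events, such as muscle soreness, can also weigh heavily in a count from 20 or 10 people.

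The summary is put to use. Section 10.0 makes the exploration of further outcomes depend on the data indicating feasibility and safety, and it uses the pilot to inform a larger trial. The midpoint comparison feeds a discussion of early stopping. If that test treats events as independent observations, its nominal error rate does not hold when events recur within a person.

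**Working it through.** The plan gives no adverse event rate, safety threshold or safety power figure, so there is no figure of its own to reproduce. The event rates and risks below are assumptions.

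**Inputs from the documents.** N = 30 (Section 4.3.1); allocation 2:1 (Sections 4.1 and 4.3.4 Randomization); 24 weeks in both arms (Section 4.1); loss-to-follow-up benchmark below 40% (Section 10.0).

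**Step 1. Arm sizes.** 30 × 2/3 = 20 exercisers; 30 × 1/3 = 10 controls. With equal follow-up, planned person-time is also 2:1.

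**Step 2. Raw counts at equal risk.** With r events per person in both arms, the count ratio is 20r / 10r = 2.0 for any r. At r = 1 it is 20 against 10 events; at r = 3, 60 against 30.

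**Step 3. The percent, under each reading, at equal risk.**

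| Reading of percent | Exercise | Control | Ratio |
|---|---|---|---|
| Share of all events | 20/30 = 66.7% | 10/30 = 33.3% | 2.0 |
| Participants with at least one event (risk 0.4 assumed) | 8/20 = 40% | 4/10 = 40% | 1.0 |
| Share of the arm's own events in a severity, seriousness or attribution class | equal if the mix is equal | equal if the mix is equal | 1.0 |

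Under the first reading, halving the rate in exercisers gives (20 × 0.5) / (20 × 0.5 + 10) = 50%, an apparently neutral split. Under the second, risks of 0.2 (4/20, 2/10) and 0.6 (12/20, 6/10) also give a ratio of 1.0.

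**Step 4. Uneven follow-up.** Assume that dropouts contribute half their follow-up. Loss of 40% among exercisers only gives 20 × 0.8 = 16 against 10: ratio 1.6, share 61.5%. Loss of 40% among controls only gives 20 against 10 × 0.8 = 8: ratio 2.5, share 71.4%. Equal loss leaves 2.0.

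**Step 5. The midpoint chi-square, if events are the unit.** Let a and b be the event counts and T = a + b. Even with the correct 2:1 expectation,

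X² = (a − 2T/3)² / (2T/3) + (b − T/3)² / (T/3)

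assumes independent events. If each person's rate varies as a gamma variable with mean m and shape k, the variance of the counts is inflated by φ = 1 + m/k. The false-positive rate at nominal 5% is then about P(χ² with 1 df > 3.84/φ). For m = 1:

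| Shape k | φ | 3.84/φ | Approximate rate | Simulated rate |
|---|---|---|---|---|
| 2 | 1.5 | 2.56 | 11% | 10% |
| 1 | 2 | 1.92 | 17% | 16% |
| 0.5 | 3 | 1.28 | 26% | 24% |

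With no between-person variation, φ = 1 and the rate stays near 5%. By the same formula, m = 0.5 gives φ of 1.25 to 2 and about 8% to 17%; m = 2 gives φ of 2 to 5 and about 17% to 38%.

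**The case against.** The best defence is that the text is incomplete rather than wrong. Section 10.0 never says that the denominator is all events. Its next sentence breaks events down by severity, seriousness and attribution, so the percent may be of an arm's own events within each class, or of participants. Both readings give a ratio of 1.0 at equal risk (the first when the event mix is equal). Anyone who knows the arms are 20 and 10 can rescale a count, and Section 8.0 lists the number of participants alongside the cumulative adverse event table. The final judgement is qualitative, with no numeric threshold and no between-arm test under objective 2, in a pilot that itself concedes low power at the midpoint.

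Much of this stands, and it rules out three stronger inferences that a reader might draw.

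- *That the Section 10.0 percent necessarily doubles the apparent harm.* It does so only under the share-of-all-events reading, which the text permits but does not state.
- *That the three places contradict one another, with Appendix A based on participants.* Section 10.0's number includes the count in Section 4.2.2, and adding a percent is no contradiction. Appendix A is ambiguous about its unit, and it describes a monitoring comparison, not an endpoint definition.
- *That a proper denominator would make the comparison precise.* With an assumed mean of 1 and shape 1, the exercise share of events at equal risk has a 95% range of 41% to 89%. Converted by s / [2(1 − s)], that is still a per-participant rate ratio of about 0.35 to 4. The spread is mostly small-sample noise; the denominator corrects the centre only.

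The defence does not dispose of the count. Sections 4.2.2 and 10.0 both prescribe it, and its expected ratio of 2.0 depends on no reading of percent. That a reader can rescale informally does not settle which measure was specified in advance.

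**Conclusion.** The point holds as a missing denominator and an unstated unit. The final safety summary is expressed in events without reference to participants or person-time, and the midpoint test does not identify its unit. The raw count carries an expected ratio of 2.0 at equal risk, given 20 against 10 participants, equal follow-up and equal ascertainment. That last condition is not assured: Appendix A also picks up events during supervised sessions, which controls do not have. The 66.7% against 33.3% split is conditional on percent meaning share of all events. The inflated error rate of about 10% to 25% is conditional on events being the chi-square unit and on the assumed mean of 1 and gamma shape of 2 to 0.5. No data from the documents fix those values. The matter should be settled before the analysis because the summary informs the safety judgement and the decision about a larger trial.

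**What to change.** In Section 10.0, objective 2, define the summary for each randomised arm as the number and percent of participants with at least one adverse event, and separately with at least one serious adverse event. The denominator is all participants randomised to that arm. Give exact 95% intervals and keep the existing severity, seriousness and attribution strata. Retain raw event counts as description, optionally with events per participant-week where follow-up dates allow. The documents do not show that onset and dropout dates are recorded, so the rate should not be the main measure.

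In Section 4.2.2 and in the Appendix A midpoint comparison, make the participant with at least one event the unit, and replace the chi-square with an exact test given the small numbers. The objective 3 safety text should name the same unit. Write adverse event in full throughout, since the abbreviation list gives AE two meanings.

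The cost is a few sentences of wording; the participant-level measure uses adverse events already collected from each participant. The drawback is that a participant-level percent does not show repeated events, which the retained event counts cover.
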